9.7 Off Study

Subjects will be considered off study when all planned treatment and follow-up visits have been completed, unless death or withdrawal of consent to continue participation occurs. The end of study visit will be conducted per the schema in section 26.

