2.4 The subject participation time period

Each subject would receive treatment at the beginning of the study Day 1 (Initial treatment), Day 30 after initial treatment, Day 180 after initial treatment, 1 Year after initial treatment and every 6 months thereafter for 2 additional years. The total subject participation time period from the first to last visit will be approximately 37 months. Treatment visits are based on the Day 1 treatment visit date to the 3 year treatment visit.

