9.4 End of Intervention

Subjects will have their last PDT treatment at visit 9 which will be considered off treatment when the visit is completed.

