9.5 Follow up

There are no specific “Follow up” visits other than the Off Study (or End of Study) follow-up visit. Please refer to section 9.7 for more details.

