11.5 Description of adverse events and reporting procedures

ADVERSE EVENTS: An adverse event (AE) is any untoward medical occurrence in a patient or clinical investigation subject administered a pharmaceutical product and that does not necessarily have a causal relationship with this treatment. An AE can therefore be any unfavorable and unintended sign, symptom, or disease temporally associated with the use of a medicinal (investigational) product, whether or not related to the medicinal (investigational) product.

Any and all adverse events will be recorded on the UACC adverse events record form and reviewed by the Principal Investigator.

All adverse events will be classified using either the MedDRA term or NCI Common CTCAE version 4.02 and will address:

- Grade
- Relationship to study drug (not related, unlikely, possible, probable, definitely)
- Causality other than study drug (disease related, concomitant medication related, intercurrent illness, other)
- Date of onset, date of resolution
- Frequency of event (single, intermittent, continuous)
- Event outcome (resolved, ongoing, death)
- Action taken (none, held, dose reduced, discontinued, medication given)

SERIOUS ADVERSE EVENTS: An SAE is any untoward medical occurrence that at any dose:

- 1) Results in death;
- 2) Is life-threatening;
- 3) Requires in-patient hospitalization or prolongation of an existing hospital stay;
- 4) Results in disability persistent or significant disability/incapacity, or;
- 5) Is a congenital anomaly/birth defect.

Note: A SAE may also be an important medical event, in the view of the investigator that requires medical or surgical intervention to prevent one of the outcomes listed above.

All serious adverse events, regardless of attribution, and any deaths will be reported within 24 hours of notification of the event to the sponsor and DSMB Coordinator. All serious adverse events, regardless of attribution, and any deaths will be reported within 5 days of notification of the event to the University of Arizona Human Subjects Protection Program.

All serious adverse events will be processed by the DSMB Coordinator monthly for initial trend analysis and fully reviewed by the DSMB every six months. The DSMB coordinator will review the SAE reporting process to confirm reporting requirements are met.

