17. ANALYSIS

17.1 Safety Analysis

The primary safety outcome measures will be estimated with 95% Clopper-Pearson CI: The proportion of evaluable study participants who had a grade 3 or higher AE or any serious adverse event that's determined to be at least possibly or probably related to study treatment, or any AE which is at least possibly or probably related to study treatment that causes permanent study discontinuation. AE's will be documented and kept in the study regulatory binder and in OnCore.

Pain will be assessed on the 10 point Visual Analogue Scale (VAS), as mild (0-3), moderate (4-7) or severe (8-10). Patients will be asked to rate the pain at the beginning, midway point (approximately 8 minutes later), and at the end of each PDT session.

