26. SCHEMA OR STUDY SCHEDULE

Study Procedures	Screening/ Baseline ^A	On Study Treatment ^B								Early Termination	End of Study ^c
		Day 1	Day 30	Day 180	12 Month	18 Month	24 Month	30 Month	36 Month		
Visits	1	2	3	4	5	6	7	8	9	ET	EOS
Eligibility Verification	x										
Informed Consent	x										
Registration	x										
Medical History ^D	x										
Physical Exam ^E	x										
Concomitant medications	x	x	x	x	x	x	x	x	x		
Levulan-PDT		x	x	x	x	x	x	x	x		
Adverse events		x	x	x	x	x	x	x	x	x	
Punch Biopsy ^F		x							x		
VAS Scale ^G		x	x	x	x	x	x	x	x		
Sun Damage Scale ^H		x	x	x	x	x	x	x	x	x	x
Photographs ^I		x	x	x	x	x	x	x	x	x	x

^A Screening may be conducted within 28 days before first treatment.

^B Treatments may be conducted \pm 3 days for Day 30 treatment and \pm 30 days for Day 180, 1 year, 1.5 year, 2 year, 2.5 year, and 3 year visits respectively. Treatment visits are based on the Initial Day 1 treatment visit.

^C 3 months (\pm 30 days) after the last treatment.

^D Medical history including past medical, meds, allergies, social and HPI will be done.

^E Physical exam will consist of vital signs (blood pressure & pulse), and a full treatment area skin exam.

^F Punch biopsies will be used for karyometric analysis between baseline and end of treatment.

^G For more information about the VAS Scale, please refer to Appendix 1.

^H For more information about the Sun Damage Scale, please refer to Appendix 2.

^I For more information about digital photography, please refer to Appendix 3.

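### Subjects who complete treatment have no scheduled adverse-event check after the eighth and last PDT session

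*Combined protocol and SAP*

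**What the plan says.** - **Last treatment.** Section 9.4: "Subjects will have their last PDT treatment at visit 9 which will be considered off treatment when the visit is completed". In the section 26 schedule the PDT row has eight marks, from Day 1 to Month 36 (visits 2 to 9).
- **Visits after that.** Section 9.5 provides for no specific follow-up "visits other than the Off Study (or End of Study) follow-up visit". Footnote C to section 26 places End of Study 3 months (±30 days) after the last treatment.
- **Content of that visit.** Section 9.7: "The end of study visit will be conducted per the schema in section 26".
- **The schedule.** The row "Adverse events" is marked at visits 2 to 9 and at Early Termination. Its End of Study cell is blank. Only the sun damage scale and photographs are marked there.
- **Recording duty.** Section 11.5: "Any and all adverse events will be recorded on the UACC adverse events record form and reviewed by the Principal Investigator". The same section has serious events reported to the sponsor and the DSMB Coordinator within 24 hours of notification. Neither it nor any other section says when collection of adverse events ends.
- **Use of the data.** Section 17.1 takes as the primary safety outcome "The proportion of evaluable study participants who had a grade 3 or higher AE or any serious adverse event" considered at least possibly related to treatment, together with related events that lead to permanent discontinuation.
- **Length of participation.** Section 2.4: "The total subject participation time period from the first to last visit will be approximately 37 months".

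**The concern.** The schedule treats adverse-event assessment as a procedure to be carried out at named visits. Section 9.6 reserves Early Termination for withdrawal or an investigator's decision to end treatment, so completers do not pass through it. A completer's last scheduled enquiry is therefore at visit 9, the day of the last session. No other scheduled item fills the gap: concomitant medications are not marked at End of Study, and the physical exam is marked only at screening. The second pair of punch biopsies is also taken at Month 36. The baseline pair is followed by a check at Day 30, the final pair by none.

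Safety is part of the primary objective (section 3.1) and the stated basis of the sample size (section 16). If a related event of grade 3 or higher develops in the weeks after session 8 and is not serious, its capture depends on the subject mentioning it or staff noticing it. Any loss would bias the observed proportion downwards. Completers would also be followed less fully than subjects who leave early, and session 8 less fully than the other seven.

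**Working it through.** **1. The plan's own safety figure.** Section 16 states that with 14 evaluable patients and no events the one-sided 95% upper bound is below 20%. The exact bound for 0 of n is 1 − 0.05^(1/n). For n = 14 this is 1 − 0.05^(1/14) = 19.3%, so the figure is reproduced. It does not depend on the visit schedule.

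**2. Is the blank cell real?** Section 26 has 11 visit columns. The adverse-events row has 8 + 1 = 9 marks (eight treatment visits and Early Termination). The sun damage and photograph rows have 8 + 2 = 10 marks each and reach End of Study. The rows align on the same columns, so the blank does not look like an artefact of text extraction.

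**3. Next scheduled check after each session, for a completer.** Nominal dates; 1 year = 365 days, 6 months taken as about 183 days.

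| Session | Given at | Next scheduled check | Interval (days) |
|---|---|---|---|
| 1 | Day 1 | Day 30 | 30 |
| 2 | Day 30 | Day 180 | 180 − 30 = 150 |
| 3 | Day 180 | Month 12 | 365 − 180 = 185 |
| 4 | Month 12 | Month 18 | about 183 |
| 5 | Month 18 | Month 24 | about 183 |
| 6 | Month 24 | Month 30 | about 183 |
| 7 | Month 30 | Month 36 | about 183 |
| 8 | Month 36 | none | – |

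Seven of eight sessions have a later check. The exception is 1/8 = 12.5% of sessions, which is not a share of events.

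**4. What a mark at End of Study would add.** With a month of 30.44 days, 3 months is 3 × 30.44 = 91 days. The ±30-day window gives 61 to 121 days after session 8. All eight sessions would then have a later check.

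**5. Sensitivity of the safety result to one event (illustration only).** Assume 14 evaluable subjects and one qualifying event that goes unrecorded. The observed proportion would be 0/14 instead of 1/14 = 7.1%, and the one-sided 95% upper bound 19.3% instead of 29.7%. The second bound solves (1 − p)^14 + 14p(1 − p)^13 = 0.05. The documents give no rate from which to judge how likely such an event is.

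**6. The 37 months in section 2.4.** Screening may precede Day 1 by up to 28 days (footnote A). To visit 9: 36 + 28/30.44 = 36.9 months. To End of Study: 36 + 3 = 39 months from Day 1, or up to 39 + 28/30.44 = 39.9 months from screening. The stated figure fits a last visit at Month 36 and leaves out End of Study.

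**The case against.** The strongest reply is that the obligation to record already covers this period. Section 11.5 has no visit restriction and asks for resolution dates and outcomes. Section 9.7 keeps the subject on study through End of Study, and section 17.1 sets no time window, so a related grade 3 event after visit 9 already counts. Staff will also be rating and photographing the treated skin at End of Study. The exposed set of events is narrow:

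- Serious events have their own reporting route.
- The discontinuation component is largely unaffected once no treatment remains.
- Pain, which section 4.4 calls the most common adverse event, is scored within each session.
- The outcome is counted per participant, so a missed event matters only in a subject with no earlier qualifying event.

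Recall over 150 to 185 days after sessions 2 to 7 is itself a weak standard. The breakdown of the 37 months is also an inference, because section 2.4 does not say how the figure was obtained.

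Most of this stands, and it limits the likely size of any bias. It does not supply the missing enquiry. A duty to record an event that comes to notice does not ensure that anyone asks, and looking at the treated fields will not reveal an event that has resolved or lies elsewhere. The schedule requires the check for subjects who leave early and gives no reason to omit it for completers.

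**Conclusion.** The concern holds. If the schedule is followed as printed, a completer has no planned adverse-event assessment after session 8 or after the final biopsies, despite attending a later visit. The weakness lies in scheduled ascertainment; the duty to record remains, and events on the day of session 8 can be recorded at visit 9. The direction of any error in the primary safety proportion is downwards. Its size is unknown and probably small, given how few kinds of event are exposed. Sample size and the section 16 bound do not change.

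This rests on the section 26 table being as printed and on nominal visit dates. The discrepancy in section 2.4 is secondary, and the conclusion does not depend on it. The change should be made because it improves capture of a primary outcome at very little cost; the gap does not invalidate the trial.

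**What to change.** 1. In section 26, mark adverse events in the End of Study column.
2. In section 9.7, state that adverse events starting after visit 9 are collected through the End of Study visit and count in the primary safety outcome when they meet the section 17.1 definition. Events following the Month 36 biopsies would be recorded as adverse events but enter that outcome only if judged related to study treatment.
3. Reconcile the participation time in section 2.4 with an End of Study visit at about month 39 from Day 1.

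The cost is one mark, one or two sentences and one figure in the protocol, plus a few minutes of questioning at an existing visit for at most 16 to 20 subjects. Recall over 2 to 4 months will be imperfect for minor events. That is less of a limitation for events of grade 3 or higher, which are the ones the primary safety outcome uses.

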10. PHARMACOKINETIC STUDIES

10.1 Collection

One skin biopsy with a 4-mm punch will be taken from each forearm (treatment and non treatment sites) prior to the first session and another skin biopsy with a 4-mm punch will be taken at the end of all the sessions at 3 years, on each forearm of all patients for a total of 4 biopsies per patient. Gelfoam or 1-2 sutures will be used to close the biopsy site.

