1.3 Endpoints

- The primary endpoint will be the total number of AK/NMSC in the treatment areas compared to the control areas.
- Time to occurrence to first AK/NMSC compared to the control areas.
- Changes in karyometry from baseline in the treatment and non treatment fields.
- Changes on the sun damage scale compared to the control areas.
- Mean pain score between the treatment field locations.

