Togsverd-Bo et al [28] found that repeated PDT sessions in renal transplant patients could serve as primary prevention for skin dysplasia. In their randomized controlled trial, 15 patients with clinically normal skin received PDT red light at inclusion and at 6 month intervals. PDT significantly delayed the onset of AK compared to untreated areas. They observed AK in 63% of patients in untreated skin compared to 28% in PDT treated skin at 3 years.

These findings are further supported by molecular studies, which mirror the clinical response, showing that PDT can reverse or reduce field cancerization but that one single dose is not sufficient to achieve these results [29,30]. For example, Bagazgoitia and colleagues have shown that two or more treatments of PDT can

delay the appearance of AKs, reduce histological features of actinic damage, and decrease expression of early markers of carcinogenesis such as K1-67 and p53 [29]. Sun-damaged skin has a higher baseline expression level of p53 than non-sun-damaged skin, and p53 and p53 family members may be important mediators of cell death signaling in photodynamic therapy of cancer [32]. This again underscores the need for repeated PDT sessions with vigilant follow-up when using this field therapy for cancer prevention. In addition, karyometric analysis has been used successfully to detect nuclear changes from sun-damaged skin to actinic keratosis to squamous cell carcinoma, and to provide sensitive, quantitative method to assess the efficacy of prevention interventions [33-36].

Associated Risks

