7. STUDY PLAN

7.1 Intervention Regimen

Levulan® Kerastick® for Topical Solution will be applied to a designated area for 1 hour without occlusion prior to illumination with blue light using the standard FDA approved treatment time for the BLU-U device of 16 minutes 40 seconds. Each subject will be randomized to undergo treatment to one side face and one dorsal forearm/hand treatment, while the other side will serve as untreated control. Treatments will be conducted at the beginning of study Day 1 (Initial Treatment), Day 30 after the initial treatment (\pm 3 days), Day 180 after initial treatment (\pm 30 days), 1 year after the initial treatment (\pm 30 days), and every 6 months (\pm 30 days) thereafter for 2 additional years.

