16. STATISTICAL CONSIDERATIONS

Characteristics of study subjects will be summarized by appropriate abstract statistics, including frequency, proportion and 95% Clopper-Pearson confidence interval (CI) for the proportion for categorical variables, median, and range for continuous variables.

Evaluable subjects for safety outcome measures will be those who complete any study visits or those who discontinue the study treatments due to adverse events (AE).
Evaluable subjects for efficacy outcome measures will be those who complete all study visits. At least 15-16 evaluable subjects for each of these analyses are expected.

Primary efficacy outcome measure will be the difference in the total number of AK/NMSC in the treatment areas compared to the control areas. All unique AK/NMSC

observed during the 3 year study period will be identified and summed in each area. The statistical significance of the difference will be tested using the Wilcoxon Signed-Rank Test.

Secondary safety and efficacy measure: Time to the occurrence of the first AK/NMSC in the control versus treated areas will be estimated using the Kaplan-Meier estimate. Changes in the p53 staining from baseline to end of treatment will be evaluated using McNemar's Test. Mean pain scores (VAS) and photo damage scale global scores of the study population will be compared with each respectively using Wilcoxon Signed-Rank Test.

Sample Size Determination: Safety will be evaluated using a one-sided confidence interval (as the lower bound is not of interest). At least fourteen patients will be evaluable for safety. If none of the patients have an adverse primary safety outcome, the upper bound of a 95% one-sided confidence interval is < 20%.

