17.2 Efficacy Analysis

Number of AK/NMSC will be counted for each site using the photographs of the treatment and the control areas. AKs will be graded by thickness I-III: I = mild, slightly palpable, II = moderate, easily felt, III= severe, very thick. NMSC, including basal cell carcinoma, Bowen's disease and squamous cell carcinoma, will be diagnosis and confirmed histologically by biopsy.

Photo damage in the treatment and control fields will be assessed by the sun damage scale as: absent, mild, moderate, and severe. The scale includes 4 points: fine wrinkling, coarse wrinkling, abnormal pigmentation and global (0-10). Ratings for epidermal dysplasia will be obtained by immunohistochemistry of p53 staining of skin biopsies in the treatment areas at baseline and after the last treatment.

Time to occurrence of AK/NMSC will be calculated from the first visit to the development of an AK or NMSC in the treatment areas and in the control areas.

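### The punch site on the forearm is not fixed, mirrored or chosen without knowledge of the treated side, which leaves the secondary p53 and karyometry results open to selection bias

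*Combined protocol and SAP*

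**What the plan says.** Section 10.1 gives the limb, punch size, number and timing of the biopsies. At baseline, "One skin biopsy with a 4-mm punch will be taken from each forearm (treatment and non treatment sites) prior to the first session". At the end, "another skin biopsy with a 4-mm punch will be taken at the end of all the sessions at 3 years, on each forearm". That makes four punches per patient, one per arm and time point.

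The biopsies have two uses:

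- **Karyometry.** Section 1.3 lists "Changes in karyometry from baseline in the treatment and non treatment fields", and the footnote to the schedule in section 26 says "Punch biopsies will be used for karyometric analysis between baseline and end of treatment". Section 16 names no test for it.
- **p53.** Section 17.2 describes "immunohistochemistry of p53 staining of skin biopsies in the treatment areas at baseline and after the last treatment". Section 16 says "Changes in the p53 staining from baseline to end of treatment will be evaluated using" McNemar's test. It gives no cut-off for positive staining and adds no control-forearm comparison. Section 17.2 separates treatment areas from control areas elsewhere, so the natural reading is that p53 is assessed on the treated side only.

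On allocation, section 7.1 says "Each subject will be randomized to undergo treatment to one side face and one dorsal forearm/hand treatment", with the other side left untreated. No section says when the side is disclosed relative to the baseline punch, or that whoever chooses the site is unaware of it.

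**The concern.** A 4-mm punch samples a very small part of a forearm. Subjects enter with moderate to severe sun damage (6.1 g), so better-looking and worse-looking points can exist on the same arm. The protocol itself links appearance to one of the markers: section 4.4 states "Sun-damaged skin has a higher baseline expression level of p53 than non-sun-damaged skin". A site picked because it looks damaged is therefore expected to stain higher than a typical site on that arm.

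If the choice is free, the measured change mixes any effect of treatment with a difference in how the two sites were chosen. For p53 the exposure is direct, because the described comparison has no control arm to absorb it. For karyometry it is indirect, because both arms are sampled at both times. At stake is whether these two biomarker results, for which each patient has four punches, can be interpreted. A baseline site cannot be standardised after the punch has been taken.

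**Working it through.** **Is there a figure to reproduce?** The documents give no power, positivity rate or variance for either marker. Their only sample-size figure is the safety bound for 0 events in 14 patients: 1 - 0.05^(1/14) = 19.26%, which agrees with the stated value below 20%. It does not bear on the biopsies.

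**Inputs from the documents.** 15-16 evaluable subjects (section 16; 15 used for p53, 16 for karyometry). One punch per arm and time point (10.1). McNemar's test on treated-side p53 (16, 17.2).

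**Inputs assumed.** p53 positivity of 40% at a random site; correlation between appearance and staining of 0.3-0.8; within-patient correlation of 0-0.4; exact two-sided test at 0.05. Section 4.4 supports the direction of the link between appearance and staining, not its strength.

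**Step 1: shift from selection.** The expected maximum of k standard normal draws is 0.56 (k = 2) or 0.85 (k = 3). Choosing by appearance shifts the marker by correlation × that value, in site-to-site SD within a patient:

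- worst of 2: 0.3 × 0.56 = 0.17 to 0.8 × 0.56 = 0.45 SD
- worst of 3: 0.3 × 0.85 = 0.25 to 0.8 × 0.85 = 0.68 SD

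**Step 2: the planned test without selection.** With b subjects going from positive to negative and d the reverse, p = 2 × P(Bin(b + d, 0.5) ≤ min(b, d)), capped at 1. If sites are independent, the expected number of discordant pairs is 15 × 2 × 0.4 × 0.6 = 7.2. Five discordant pairs can never reach significance (2 × 0.5^5 = 0.0625); six all in one direction can (2 × 0.5^6 = 0.031). The test is therefore conservative.

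**Step 3: simulation with no treatment effect.** The baseline site is the worst-looking of k candidates and the 3-year site is random.

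| Baseline site | False significant fall in p53 |
|---|---|
| Unselected | about 0.5-0.9% |
| Worst of 2 | about 1-8% |
| Worst of 3 | about 2-21% |

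If the baseline site is unselected and the 3-year site is the worst-looking, the roles of b and d swap, and the same rates apply to a false rise. If both visits use the same selection, the two positivity rates are equal and the false-fall rate returns to the unselected level.

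**Step 4: karyometry.** The plan names no test, so a signed-rank test on the treated-minus-control difference in change is assumed, with 16 subjects, within-patient correlation 0.3, and appearance correlation 0.3-0.8.

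| Baseline selection | Mean difference in change | Rejection rate |
|---|---|---|
| None on either arm | about 0 | about 4-5% |
| Worst of 3-5 sites on both arms | about 0 | about 4% |
| Worst of 3-5 on treated arm, random on control | -0.2 to -0.8 SD | 7-41% |

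Only selection that differs by arm biases this comparison.

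**The case against.** The strongest reply is that nothing in the documents says the operator will pick a worse site, at either visit. That stands. A reader might infer that the plan will produce a false fall in p53. The documents do not support this: it needs a selected site at baseline and an unselected one at 3 years, and the net direction is unknown.

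A reader might also quote larger rates. A signed-rank test on a continuous staining score, with a correlation of 0.5-1.0, gives false falls in 10-35% of trials for worst of 2 and 19-65% for worst of 3. Section 16 names McNemar's test instead, and a correlation of 1.0 would mean that looking at the skin predicts staining perfectly. Those rates do not describe this plan.

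A third tempting inference is that the treated-control karyometry comparison is already compromised. It is not, unless site choice differs by arm.

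The entry rules also help: 6.1 e and f bar prior skin cancer and recent actinic keratosis or Bowen's disease in the treatment fields, so picking an overt lesion on the treated arm at baseline is limited. They do not cover the control forearm, uneven sun damage, or lesions that develop over 3 years.

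Finally, this is a pilot, p53 is not in the endpoint list of section 1.3, and the primary endpoint is a lesion count. All of that stands and limits the weight of the point. It does not close the gap in 10.1.

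**Conclusion.** The concern holds as a cheap improvement affecting secondary biomarkers only. Section 10.1 leaves the site within the forearm open at both visits, and no other section closes it. This allows p53 to be biased in either direction, and karyometry to be biased if the arms are sampled differently.

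For p53, the false-fall rate could rise from under 1% to about 1-8% or 2-21%, depending on whether the baseline site is the worst of 2 or of 3. These ranges rest on the assumed 40% positivity, the assumed correlations, and one particular pattern of choice. They illustrate what the plan permits and are not a forecast. The primary comparison of lesion counts is unaffected.

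**What to change.** **In 10.1:**

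- Take the baseline punches at mirror-image points on the two dorsal forearms, at a set distance from a landmark. Mark and photograph them before the treated side is disclosed.
- Take the 3-year punches at a preset offset from the baseline scar, in the same direction on both arms, whatever the skin looks like. This also keeps the second punch out of the scar. The rule governs only the research punch.
- Record any forced move, and repeat the p53 and karyometry analyses without those subjects.

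**In 17.2:** stain the control-forearm biopsies for p53 as well, and compare the change between arms, so that selection common to both arms cancels.

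**Cost:** a paragraph in 10.1 and a sentence in 17.2, a measurement at two visits where photographs are already scheduled (section 26), p53 staining of control specimens already collected, and occasional forced moves. No extra biopsy or visit is needed.
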